5.1.3. Period 3: Double-Blind, Long-Term Extension

Patients who complete the study through Week 52 will progress into the double-blind long-term extension phase through Week 104 (Visit 22). Daily diary collection will continue through Week 68 (Visit 18) of Period 3.

Concomitant use of background TCS therapy will continue during this treatment period as described in Section 7.7.2.

5.1.3.1. Randomized Downtitration Substudy at Week 52

At Week 52, all patients will be evaluated for substudy eligibility. To be eligible, a patient must meet all of the following criteria:

- have an IGA 0, 1 (Responder) or 2 (Partial responder) at Week 52
- have not used high- or ultra-high potency TCS in the last 14 days (potency classification in [Appendix 7](#))
- do not currently have study drug interrupted
- have been assigned to baricitinib 2-mg or 4-mg at baseline (assessed by interactive web-response system [IWRS])

Treatment

Treatment in the substudy is illustrated in [Figure JAIN.1](#). Patients eligible for the substudy will be rerandomized at a 1:1 ratio at Week 52 based on the baricitinib treatment group assigned at baseline:

- 4-mg QD rerandomized to baricitinib 4-mg QD, or baricitinib 2-mg QD
- 2-mg QD rerandomized to baricitinib 2-mg QD, or baricitinib 1-mg QD

Note: Intensification of emollients and TCS may be continued or initiated to control worsening and unacceptable symptoms of AD any time during this treatment period. For management of TCS, follow the guidelines in [Section 7.7.2](#).

Retreatment

During the substudy, if worsening of AD symptoms occurs such that IGA increases to ≥ 3 , the patient will be automatically retreated with their presubstudy baricitinib dose. When the IGA is ≥ 3 , the investigator should reinstate background TCS therapy (e.g., triamcinolone 0.1% cream and/or hydrocortisone 2.5% ointment), provided the patients are not currently using TCS, and may prescribe high- or ultra-high-potency TCS following the guidelines for use of Rescue Therapies ([Section 7.7.5](#) [Rescue Therapy]). An unscheduled visit may be needed to assess worsening of symptoms and to perform clinical safety and efficacy assessments immediately before retreatment.

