Patients whose disease cannot be controlled by the measures described above may be rescued to systemic therapies (conventional systemics or biologics). These patients will be required to discontinue investigational product and proceed to the ETV before initiating systemic treatment. However, patients rescued to systemic therapies prior to the primary endpoint (Week 16) should be encouraged to continue with study visits and assessments through Visit 8.

7.7.5.2. Rescue during Periods 3 and 4: from Week 52 (Visit 14) to Week 200 (Visit 28)

In Period 3, all patients will continue to use concomitant background TCS (e.g., triamcinolone 0.1% cream and hydrocortisone 2.5% ointment) as described in Section 7.7. In Period 4, use of concomitant may continue as directed by the investigator, as per clinical practice. All patients may be rescued at any time with high- or ultra-high-potency TCS or phototherapy as described in Section 7.7.

As mentioned in Sections 5.1.3 and 5.1.4, patients who reach an IGA ≥ 3 after entry into the randomized downtitration substudy will be automatically retreated with their presubstudy dose of baricitinib.

Patients not eligible for the substudy and who present with an IGA ≥ 3 at Week 52 or anytime thereafter will automatically be rerandomized at a 1:1 ratio to baricitinib 2-mg QD or baricitinib 4-mg QD, but this will only occur once. Patients randomized to baricitinib 4-mg QD at baseline (Week 0, Visit 2) will stay on this dose for the remainder of the trial regardless of IGA.

Patients whose disease cannot be controlled by the measures described above may be rescued to systemic therapies (conventional systemics or biologics). Whenever possible during this Period, it is recommended to wait for at least 4 weeks after the visit at which the patient has reached IGA ≥ 3 to initiate rescue with systemic therapies.

Patients rescued with high- or ultra-high-potency TCS will continue to take investigational product and use of topical rescue therapy will be documented in the eCRF.

Patients rescued with phototherapy will remain in the trial and will be required to temporarily interrupt the use of investigational product until completion of the phototherapy.

Patients who need rescue with systemic therapies (conventional systemics or biologics) during Period 3 will be required to discontinue investigational product and to proceed to the ETV before initiating systemic treatment.

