10.3.1.1. Missing Data Imputation

- Nonresponder imputation (NRI): All patients who discontinue the study or the study treatment at any time for any reason will be defined as nonresponders for the NRI analysis for categorical variables such as IGA 0/1 or EASI50/75/90 from the time of discontinuation and onward. Patients who receive rescue therapy (high or ultra-high potency TCS, phototherapy, or systemic therapies for treatment of AD, see Section 7.7.5) will be analyzed as nonresponders from the point of rescue and onward. An additional analysis will be performed that includes all available data regardless of whether rescue medication was given or not.
- Continuous variables such as EASI and SCORAD scores will be assumed to be missing from the point of rescue or discontinuation and then an MMRM analysis will be performed. An additional analysis will be performed that includes all available data regardless of whether rescue medication was given or not.
- Last observed carried forward: An additional analysis will be performed that uses the last observed value prior to discontinuation or rescue therapy. This will then be analyzed using a logistic model for categorical variables or ANCOVA for continuous variables as described above.

There will be further discussion on the relevant estimands including appropriate methods for analysis and imputation of missing data in the SAP. This will include specifications of additional sensitivity analyses for the primary and key secondary endpoints such as tipping point as well as a reference-based multiple imputation method.

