For **Long-Term Extension(LTE) Substudy analysis**, the censoring rule will censor the efficacy and health outcome results after permanent study drug discontinuation or after the retreatment, whichever occurred first.

For **Long-Term Extension(LTE) Non-responder analysis** the censoring rule will censor the efficacy and health outcome results after permanent study drug discontinuation.

For **Time to Relapse analysis**, if Relapse (IGA $\geq 3$  in Period 3 or Period 4) occurred on or after permanent study drug discontinuation, the event would be censored on the last available visit date.

For **Long-Term Extension (LTE) Responders & Partial Responders who did not enter the Substudy** the censoring rule will censor the efficacy and health outcome results after permanent study drug discontinuation or after the dose change, whichever occurred first.

Nonresponder imputation (for categorical variables) and MMRM (for continuous variables) will be the primary methods used to handle missing data. Sections 6.3.1 through 6.3.5 summarize the imputation methods for the various efficacy and health outcome endpoints.

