**Table JAIN.6.4. Imputation Techniques for Various Variables**

Efficacy and Health Outcome Endpoints for 24-week interim analyses	Imputation Method
IGA (0,1), EASI75, 4-point Itch NRS improvement	NRI a,b , pMI a , Tipping point a
EASI90, SCORAD75	NRI a,b , pMI a
EASI percent change, ADSS Item 2 change, Skin Pain NRS change	MMRM a,b , mLOCF a , pMI a , mBOCF a
All remaining categorical measures	NRI a
All remaining continuous efficacy and health outcome measures	MMRM a , mLOCF a
Efficacy and Health Outcome Endpoints for 52-week interim analyses	
IGA (0,1), EASI75, 4-point Itch NRS improvement	NRI a,b
EASI90, SCORAD75	NRI b
IGA(0,1,2), EASI <=7, SCORAD <=25, DLQI <=5	NRI a,b
All remaining categorical measures	NRI b
EASI percent change, ADSS Item 2 change, Skin Pain NRS change	MMRM b , mLOCF b
All remaining continuous efficacy and health outcome measures	MMRM b , mLOCF b
Efficacy and Health Outcome Endpoints for Period 3 and/or Period 4 analyses	
IGA (0,1), EASI75, 4-point Itch NRS improvement	mLOCF c
All remaining categorical measures	mLOCF c
EASI percent change, ADSS Item 2 change, Skin Pain NRS change	mLOCF c
All remaining continuous efficacy and health outcome measures	mLOCF c

Abbreviations: ADSS = Atopic Dermatitis Sleep Scale; EASI = Eczema Area and Severity Index score; EASI75 = 75% improvement from baseline in Eczema Area and Severity Index score; EASI90 = 90% improvement from baseline in Eczema Area and Severity Index score; IGA = Investigator's Global Assessment for AD; mBOCF = modified baseline observation carried forward; mLOCF = modified last observation carried forward; MMRM = mixed model repeated measures; NRI = nonresponder imputation, NRS = Numeric Rating Scale; pMI = placebo multiple imputation; SCORAD75 = 75% decrease from baseline in Scoring Atopic Dermatitis values.

Notes: missing data related to COVID-19 may be imputed using the method specified in Section 6.3.7.

a Analyses utilizing the primary censoring rule.

b Analyses utilizing the secondary censoring rule.

c Analyses utilizing the Long-Term Extension Substudy censoring rule, or Long-Term Extension Non-responder censoring rule.

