**Table JAIN.6.9. Description of Primary, Secondary, and Exploratory Efficacy Analyses (Period 3 and Period 4)**

Measure	Variable	Population (Section 6.2.1)	Analysis Method (Section 6.2.2)	Time Point	Baseline definition
Validated Investigator's Global Assessment for AD (IGA)	Proportion of patients with a response of IGA 0 or 1	LTE Substudy Population	Descriptive using Obs and mLOCF	Weeks 52-200	N.A.
		LTE Substudy Population – Patients with IGA of 0 or 1 at Week 52	Descriptive using Obs and mLOCF	Weeks 52-200	
		LTE Non-responder Population	Descriptive using Obs and mLOCF	Weeks 52-200	
	Proportion of patients with a response of IGA 0, 1, or 2	LTE Responder & Partial Responders who did not enter the substudy	Descriptive using Obs and mLOCF	Weeks 52-200	
	Time to relapse (time to IGA $\geq 3$ )	LTE Substudy Relapse Population	
 
Descriptive
 
Kaplan-Meier plot
 
	Downtitration and withdrawal period	N.A.
	Proportion of patients with a response of IGA(0, 1), IGA(0, 1, 2) within 16 weeks of Disease Retreatment	LTE Substudy Relapse Population	Descriptive	Downtitration and withdrawal period	N.A.
Eczema Area and Severity Index (EASI)	Proportion of patients achieving EASI75 (achieving EASI percent change from baseline $\leq -75$ )	LTE Substudy Population	Descriptive using Obs and mLOCF	Weeks 52-200	Week 0 Baseline
		LTE Substudy Population - Patients with IGA of 0 or 1 at Week 52	Descriptive using Obs and mLOCF	Weeks 52-200	Week 0 Baseline
		LTE Non-responder Population	Descriptive using Obs and mLOCF	Weeks 52-200	Week 0 Baseline

Measure	Variable	Population (Section 6.2.1)	Analysis Method (Section 6.2.2)	Time Point	Baseline definition
	Proportion of patients achieving EASI50	LTE Responder & Partial Responders who did not enter the substudy	Descriptive using Obs and mLOCF	Weeks 52-200	Week 0 Baseline
	Proportion of patients achieving EASI90				
Eczema Area and Severity Index (EASI)	Change from baseline in EASI score	LTE Substudy Population	Descriptive using Obs and mLOCF	Weeks 52-200	Week 0 Baseline
	Percent change from baseline in EASI score	LTE Substudy Population – Patients with IGA of 0 or 1 at Week 52	Descriptive using Obs and mLOCF	Weeks 52-200	Week 0 Baseline
		LTE Non-responder Population	Descriptive using Obs and mLOCF	Weeks 52-200	Week 0 Baseline
		LTE Responder & Partial Responders who did not enter the substudy	Descriptive using Obs and mLOCF	Weeks 52-200	Week 0 Baseline

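### The down-titration substudy analysis ignores potent topical steroid and phototherapy rescue, and no parallel analysis counts such rescue as nonresponse

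*SAP*

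**What the plan says.** SAP 6.3 gives the substudy its own censoring rule: "the censoring rule will censor the efficacy and health outcome results after permanent study drug discontinuation or after the retreatment, whichever occurred first". Rescue is not in the list. Table JAIN.6.4 assigns mLOCF to every Period 3/4 endpoint with footnote c alone ("Analyses utilizing the Long-Term Extension Substudy censoring rule, or Long-Term Extension Non-responder censoring rule"). Footnote a (the primary rule, which censors at rescue) and footnote b (the secondary rule, which keeps data after topical or phototherapy rescue) do not appear in those rows. Table JAIN.6.9 lists the substudy IGA and EASI response endpoints as "Descriptive using Obs and mLOCF".

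On rescue in Periods 3 and 4, Protocol 7.7.5.2 says: "All patients may be rescued at any time with high- or ultra-high-potency TCS or phototherapy as described in Section 7.7". Study drug continues after topical rescue and is only interrupted for phototherapy. Retreatment with the pre-substudy dose (Protocol 5.1.3.1) needs an IGA of 3 or more.

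On the analysis of rescued patients, Protocol 10.3.1.1 names potent TCS, phototherapy and systemic therapy and says that such patients "will be analyzed as nonresponders from the point of rescue and onward". An analysis of all data regardless of rescue is an addition to that. The section is not limited to Period 2. SAP 6.3 also says that the primary censoring rule covers all efficacy endpoints, and SAP 6.3.1 says that all categorical endpoints use nonresponder imputation (NRI) under it.

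**The concern.** The substudy asks whether efficacy holds on a lower dose combined with TCS (Protocol 5.4). Potent TCS is considered when lesions persist or worsen despite background treatment (Protocol 7.7.2). A patient kept at IGA 2 or below by that rescue is a different result from one who stays there without it, yet both enter the Week 68 and Week 104 proportions as responders. No tests are planned for Periods 3 and 4, so those proportions are the whole result.

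The SAP also makes the distinction just before the substudy starts. At Week 52, Table JAIN.6.4 lists IGA(0,1), IGA(0,1,2) and EASI75 under both censoring rules. From Week 52 onward, the rescue-sensitive version of the same endpoints is dropped without a stated reason.

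**Working it through.** **Trace of one patient.** Take a substudy patient at IGA 2 who receives potent TCS or phototherapy and stays below IGA 3.

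| Question | Source | Answer |
|---|---|---|
| Is the rescue allowed? | Protocol 7.7.5.2 | Yes, at any time |
| Is study drug permanently stopped? | Protocol 7.7.5.2 | No: continued (TCS) or interrupted (phototherapy) |
| Is the patient retreated? | Protocol 5.1.3.1 | No: IGA is below 3 |
| Is the later IGA or EASI value censored? | SAP 6.3, substudy rule | No: neither event has occurred |
| How is it counted? | Tables JAIN.6.4 and JAIN.6.9 | As observed; mLOCF can carry it forward after a later discontinuation (SAP 6.3.3) |
| How would Protocol 10.3.1.1 count it? | Protocol 10.3.1.1 | Nonresponder from rescue |

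The gap covers rescue with IGA below 3 before and after. Systemic rescue is outside it, because study drug must then be stopped. If an assessment just before rescue, which Protocol 7.7.5 asks for, shows IGA 3 or more, retreatment and censoring follow.

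**Conflict within the SAP.** The general statements in 6.3 and 6.3.1 (primary rule and NRI for all categorical endpoints) cannot both hold with footnote c and mLOCF in Table JAIN.6.4. The specific table entry presumably governs, but the SAP does not say so.

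**Size.** The plan has no figure on this point: it gives neither a substudy rescue rate nor a substudy power. The illustration below therefore rests on assumed values.

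- m = response rate with rescue counted as nonresponse: 70% staying on dose, 50% on the lower dose (difference 20 points).
- r = share rescued topically or by phototherapy and not retreated.
- q = share of those who read as responders: 80%.
- Rate under the SAP rule = m + r × q.

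| r, stay | r, lower | Stay-on-dose rate | Lower-dose rate | Difference |
|---|---|---|---|---|
| 5% | 5% | 0.70 + 0.05 × 0.8 = 74% | 0.50 + 0.05 × 0.8 = 54% | 20 points |
| 5% | 15% | 74% | 0.50 + 0.15 × 0.8 = 62% | 12 points |
| 5% | 25% | 74% | 0.50 + 0.25 × 0.8 = 70% | 4 points |
| 10% | 30% | 0.70 + 0.10 × 0.8 = 78% | 0.50 + 0.30 × 0.8 = 74% | 4 points |

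Equal rescue raises both rates and leaves the difference unchanged. Unequal rescue narrows it.

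**Arm size.** The planned 100 patients on 4 mg and 200 on 2 mg, split 1:1, give at most 50 and 100 per substudy arm. One reclassified patient moves an arm by at least 1/50 = 2 points or 1/100 = 1 point, and by more if fewer patients qualify.

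**The case against.** The strongest reply is that this is a legitimate treatment-policy analysis. The secondary rule, which keeps data after topical rescue, is already the main rule at Week 52 (SAP 6.3). The substudy is about baricitinib combined with TCS, and Protocol 10.3.1.1 leaves further discussion of estimands to the SAP. Counting nonresponse from first rescue onward is also severe: potent TCS may be used for up to 14 consecutive days (Protocol 7.7.5.1), so a short course begun at Week 54 would still count as failure at Week 104, 50 weeks later. This stands as a reason to keep the current analysis. It does not explain why the substudy has no stated estimand, or why the second analysis stops at Week 52. The rescue summary in SAP 6.10.1 is by visit and type; it is not specified by substudy arm or linked to response.

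Some stronger readings are tempting but unsupported:

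- Entry requires that patients "have not used high- or ultra-high potency TCS in the last 14 days". A reader might infer that the plan rejects a rescued response at Week 52 and accepts it at Week 68. The criterion bars entry only: SAP 6.2.1 still calls these patients responders or partial responders.
- The protocol also allows this: "Intensification of emollients and TCS may be continued or initiated to control worsening and unacceptable symptoms of AD any time during this treatment period". Stepping up background TCS is not rescue under Protocol 10.3.1.1, so it is not part of this point.
- At IGA 3 or more the investigator "may prescribe high- or ultra-high-potency TCS following the guidelines for use of Rescue Therapies". A reader might extend the fault to response after retreatment. The quoted rule ends at retreatment and does not govern that endpoint.
- Time to IGA 3 or more might look misdefined because rescue is not an event. It is the protocol's own endpoint, and the SAP follows it.

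**Conclusion.** The gap is established from the text. Topical and phototherapy rescue below IGA 3 triggers neither censoring nor nonresponse in the substudy, which departs from Protocol 10.3.1.1 and conflicts with the general statements in SAP 6.3 and 6.3.1. Each arm's maintenance rate is higher than under the protocol rule, by an amount that the documents do not allow one to compute.

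A reader might infer that the comparison is biased in favor of down-titration. That holds only if rescue is more frequent on the lower dose, which is plausible because rescue follows worsening but is not shown; the 4- to 12-point differences above rest on it. Nor do the documents show that the current rule is wrong in itself, since it is one of two defensible estimands. Because Periods 3 and 4 are descriptive and unadjusted for multiplicity, what is at stake is interpretation of the substudy, and no error rate is affected. The missing analysis is cheap and bears directly on what the substudy can conclude.

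**What to change.** 1. In SAP 6.3 and 6.3.1, state which rule governs the substudy and reconcile the text with Table JAIN.6.4, including NRI versus mLOCF.
2. Keep the current analysis, state its estimand, and label it *regardless of topical rescue*.
3. Add to Table JAIN.6.9 a parallel descriptive analysis of IGA 0/1, IGA 0/1/2 and EASI75 at Weeks 68 and 104, counting patients as nonresponders from rescue onward as in Protocol 10.3.1.1.
4. Tabulate rescue by substudy arm and type.

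Two supplementary displays are optional and would not replace protocol endpoints: time to IGA 3 or more or rescue, whichever is first, and response after retreatment split by rescue use.

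The cost is SAP wording and a few tables; Protocol 7.7.5.2 already requires topical rescue to be documented in the eCRF. Maintenance rates in the added analysis will be the same or lower. SAP Version 5 concerns the final lock and follows the Week 104 lock, so an analysis added now must be labeled post hoc. No clinical rescue or retreatment rule changes.

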All Patients Entering the Substudy To evaluate the change in clinical response after treatment downtitration from baricitinib	
 
• 4-mg to 2-mg compared with patients who are rerandomized to remain on baricitinib 4-mg
 
• 2-mg to 1-mg compared with patients randomized to remain on baricitinib 2-mg
 

Patients Entering the Substudy with IGA 0 or 1 To evaluate the change in clinical response after treatment downtitration from baricitinib	
 
• 4-mg to 2-mg compared with patients who are rerandomized to remain on baricitinib 4-mg
 
• 2-mg to 1-mg compared with patients randomized to remain on baricitinib 2-mg
 

Patients Retreated during Substudy To evaluate the ability to recapture efficacy based on clinical measures after experiencing a loss of treatment benefit:	
 
• Proportion of patients with a response of IGA 0, 1, or 2 within 16 weeks of retreatment
 
• Proportion of patients with a response of IGA 0 or 1 within 16 weeks of retreatment
 
• Proportion of patients with a response of EASI75 from baseline of originating study within 16 weeks of retreatment
 

Patients Not Entered into Substudy These are prespecified objectives that will not be adjusted for multiplicity	
All Patients To evaluate the long-term effect of baricitinib dose on clinical measures	
 
• Proportion of patients with a response of IGA 0, 1, or 2 assessed at Weeks 68 and 104
 
• Proportion of patients with a response of IGA 0 or 1 assessed at Weeks 68 and 104
 
• Proportion of patients with a response of EASI75 assessed at Weeks 68 and 104
 

Patients with IGA 0 or 1 To evaluate the long-term effect of baricitinib dose on clinical measures	
Non-responder Patients at Week 52	

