### **6.2.2. General Considerations for Analyses for the 24-Week, 52-Week, , 104-Week Interim Analysis, and Final DBL**

**Period 2** starts at randomization (Visit 2, Week 0) and ends with the visit at Week 52 (Visit 14) or the early discontinuation visit (between Weeks 0 and 52).

**24-week interim analysis** will be done when all the patients complete Week 24 assessment (Visit 10) or discontinue study or treatment before the Week 24 assessment.

**52-week interim analysis** will be done when all the patients complete Week 52 assessment (Visit 14) or the early termination visit (between Weeks 0 and 52).

**Period 3** starts at re-randomization (Visit 14, Week 52) and ends with the visit at Week 104 (Visit 22) or the early discontinuation visit (between Weeks 52 and 104).

**104-week interim analysis** will be conducted when all the patients complete Week 104 assessment (Visit 22) or the early termination visit (between Weeks 0 and 104).

**Period 4** starts at (Visit 22, Week 104) and ends with the visit at Week 200 (Visit 28) or the early termination visit (between Weeks 104 and 200). For the final DBL, efficacy endpoints beyond week 104 will be exploratory in nature and will be analyzed in a descriptive way using observed data.

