### **6.3.3. Modified Last Observation Carried Forward**

A modified last observation analysis is performed by carrying forward the last postbaseline assessment for the continuous measures, assuming that effects of treatments remain the same after the occurrence of the intercurrent event (after application of the primary censoring rule). After mLOCF imputation, data from patients with non-missing baseline and at least 1 postbaseline observation will be included in the analyses. These mLOCF analyses help ensure that the maximum number of randomized patients who were assessed postbaseline will be included in the analyses.

For patients who experience any intercurrent event at any time, the last non-missing postbaseline observation on or prior to this event will be carried forward to subsequent time points for evaluation. If a patient does not have a non-missing observed record (or one imputed by other means) for a postbaseline visit prior to discontinuation or rescue, the last postbaseline record prior to the missed visit will be used for the visit.

For patients who entered the Period 3 and Period 4 treatment, the mLOCF in Period 3 and Period 4 will be performed by carrying forward the last available assessment if the treatment dosage did not change at the time of the last available assessment, which could be the assessment in Period 2, Period 3, or Period 4. If a patient was re-randomized at Week 52 and the treatment dosage

changed on/after Week 52, the mLOCF will be performed by carrying forward the last available assessment after the dosage change (Week 52), and before the censoring rule's cut-off date. The observed values after the censoring rule's cut-off date (i.e., retreatment such as dose up-titrated back to presubstudy dose) will not be carried forward. If Week 52's value is used as the Baseline, then the post-baseline (after Week 52) value could be carried forward to subsequent time points for evaluation.

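### In the down-titration substudy, the observed IGA 0/1/2 percentage leaves out patients already retreated, and the wording of the companion mLOCF rule does not ensure that relapses count as failures

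*SAP*

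**What the plan says.** Protocol Section 5.1.3.1 provides that once IGA reaches 3 or more in the substudy, "the patient will be automatically retreated with their presubstudy baricitinib dose". It asks for efficacy to be assessed immediately beforehand, at an unscheduled visit if necessary. SAP Table JAIN.6.3 shows that this covers both re-randomised arms: patients who stayed on their dose also have a retreatment step, at the same dose. SAP Section 6.3 then sets the substudy rule: "the censoring rule will censor the efficacy and health outcome results after permanent study drug discontinuation or after the retreatment, whichever occurred first".

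SAP Table JAIN.6.9 plans the substudy IGA and EASI summaries for Weeks 52 to 200 as "Descriptive using Obs and mLOCF". Table JAIN.6.4 lists mLOCF as the only imputation for Periods 3 and 4. For the final lock, however, Section 6.2.2 says that "efficacy endpoints beyond week 104 will be exploratory in nature and will be analyzed in a descriptive way using observed data".

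Section 6.3.3 describes mLOCF in two ways. In general, "the last non-missing postbaseline observation on or prior to this event will be carried forward". For patients re-randomised to a different dose at Week 52, which means the down-titrated arms, it specifies "carrying forward the last available assessment after the dosage change (Week 52), and before the censoring" rule's cut-off date. The next sentence bars only values after that date.

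Sections 6.3 and 6.3.1 name nonresponder imputation as the primary method for categorical endpoints. Section 4.2.2 adds a recapture objective: "To evaluate the ability to recapture efficacy based on clinical measures after experiencing a loss of treatment benefit". Section 6.2.2.3 limits Periods 3 and 4 to descriptive statistics, without tests.

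**The concern.** The event that triggers censoring is itself failure on the endpoint scale. IGA 3 or above is both nonresponse for IGA 0/1/2 and the trigger for retreatment. Anyone still contributing observed data at a visit has therefore been at IGA 2 or below at every earlier assessed extension visit. Earlier relapsers have left the numerator and the denominator.

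The substudy asks whether a lower dose maintains response. With no test planned, the percentages are the result. A reader comparing observed percentages at Week 68 or Week 104 could conclude that the lower dose holds response when many patients have already gone back to their previous dose. The mLOCF column protects against this only if the relapse value is the one carried forward, and the SAP does not say so consistently.

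**Working it through.** The documents state no relapse rate, response rate or sample size for the substudy, so there is no figure of theirs to reproduce. The relapse rates and their timing below are assumptions.

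**Inputs.** Scheduled visits after re-randomisation are Weeks 56, 60, 64, 68, 76, 84, 92 and 104 (Protocol Schedule of Activities), at intervals of 4, 4, 4, 4, 8, 8, 8 and 12 weeks, 52 in total. Assumed cumulative relapse *c* by Week 104 is 60% (down-titrated) and 30% (stay). No dropout; every relapse is found at a scheduled visit.

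**Formulas.** If a visit interval carries a share *w* of the total log-survival:
- observed IGA 0/1/2 at that visit = (1 − *c*)^*w*, which is one minus new relapses among those not yet retreated;
- response with every retreated patient counted as a failure = 1 − cumulative relapse.

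**Week 104.** A constant hazard in calendar time gives *w* = 12/52. A front-loaded pattern (shares 12, 10, 8, 6, 5, 4, 4, 3 out of 52) gives *w* = 3/52.

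| Summary at Week 104 | Down-titrated | Stay | Difference |
|---|---|---|---|
| Retreated patients as failures | 40.0% | 70.0% | 30 points |
| Observed, constant hazard | 0.4^(12/52) = 80.9% | 0.7^(12/52) = 92.1% | 11 points |
| Observed, front-loaded | 0.4^(3/52) = 94.9% | 0.7^(3/52) = 98.0% | 3 points |

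Under the constant hazard the observed denominators at Week 104 are 49.4% and 76.0% of the arms.

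**Week 68.** With the same rates and a constant hazard, observed response is 93.2% vs 97.3% (4 points). Counting retreated patients as failures gives 75.4% vs 89.6% (14 points). As a second illustration, take 40% vs 20% relapse by Week 68 with equal risk at each of four visits. Observed response is 0.6^(1/4) = 88.0% vs 0.8^(1/4) = 94.6%, so 20 points becomes 6.6.

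**Unscheduled visits.** SAP Sections 6.2 and 6.2.2.1 bring an unscheduled value into a by-visit summary only when the scheduled value is missing and the date falls inside the window. If every relapse were found outside a window, observed IGA 0/1/2 would be 100% in both arms.

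**mLOCF, two readings at Week 104.**
- Relapse-visit value carried: 40% vs 70%, the full 30 points.
- Strict *before*, with assessment and retreatment on the same date: the relapse value is dropped in the down-titrated arms, and the previous IGA of 2 or below is carried. That gives 100% among down-titrated patients with a usable value. The stay arms fall under a different sentence and remain at 70%. If the same-day value still counted at its own visit and only could not be carried further, the down-titrated figure under the constant hazard would be 1 − (0.494 − 0.400)/0.932 = 89.9%, still above 70%. Here 0.932 is the share not relapsing at the first visit, since those who do relapse then have nothing to carry.

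**The case against.** The best defence is that the observed summary is only one of two. Table JAIN.6.9 pairs it with mLOCF, which keeps retreated patients. Three texts favour carrying the relapse value: Section 6.3 censors results *after* retreatment, the general mLOCF rule includes the value on the event date, and the dose-change paragraph expressly bars only later values. On that reading mLOCF shows 40% vs 70%, and nothing is hidden up to Week 104. This stands as the more natural reading, but one sentence that applies only to the down-titrated arms points the other way.

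Several stronger readings are tempting and are not supported:
- *Retreated patients are deleted from all response summaries.* They are not; mLOCF retains them.
- *Observed response stays high whatever the relapse.* It does fall. With 80% relapse by Week 104 and a constant hazard it is 0.2^(12/52) = 69.0%.
- *All three substudy endpoints are affected alike.* A patient at IGA 2 is not retreated and stays in the observed denominator as an IGA 0/1 nonresponder, and EASI75 is not the trigger.
- *The SAP breaches Protocol Section 10.3.1.1.* That section says "All patients who discontinue the study or the study treatment at any time for any reason will be defined as nonresponders", but for the nonresponder analysis. It also plans a last-observation analysis and leaves further methods to the SAP. The conflict that remains is inside the SAP, between Sections 6.3 and 6.3.1 and Table JAIN.6.4.
- *The recapture data are deleted.* Recapture has its own relapse population, treatment sequences and table row. What is missing is an explicit exemption.

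It can also be said that relapse is reported separately. However, Section 6.10 and Table JAIN.6.9 place time to relapse and its Kaplan-Meier plot in patients who relapsed. As written, these cannot show what proportion of each re-randomised arm lost response.

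**Conclusion.** The point holds in a limited form. The observed IGA 0/1/2 summary measures relapse at a visit, not cumulative loss of response. It would turn an assumed 30-point difference at Week 104 into roughly 3 to 11 points, depending on relapse timing. It is one of two summaries up to Week 104 and, under Section 6.2.2, the only one afterwards, although Table JAIN.6.9 lists both through Week 200. The mLOCF summary recovers the full difference only if the relapse-visit value is carried. A strict reading of the dose-change sentence drops it in the down-titrated arms alone and could reverse the comparison. mLOCF can also carry a response past permanent discontinuation of study drug, despite the SAP naming nonresponder imputation as the primary categorical method.

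The sizes rest on assumed relapse rates and timing; the compression itself follows from the rules. No error rate is affected, because Periods 3 and 4 are descriptive and unadjusted and efficacy after Week 104 is exploratory. This is a should-fix.

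**What to change.** 1. In SAP Section 6.3.3, change *before* to *on or before* the cut-off date for patients whose dose changed, so that the IGA assessment that triggered retreatment is carried forward.
2. For categorical substudy endpoints, add a nonresponder analysis as the main summary. The denominator is all substudy entrants in each re-randomised arm, and a patient is a nonresponder from retreatment or permanent discontinuation of study drug onward. This differs from item 1 where it matters: a patient at IGA 3 could still meet EASI75 when retreated, and mLOCF would carry that as a response. Keep observed data as supplementary, with the number already retreated beside each percentage at every visit, including after Week 104. Reconcile Section 6.2.2 with Table JAIN.6.9 for that period.
3. State that retreatment censoring does not apply to the recapture endpoint.

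The cost is SAP wording and re-programming of some descriptive tables; no new data are needed. The reported response percentages will be lower.
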